### Two group t-test of equivalence in means (equal n's)

	1
Test significance level,	0.025
$\alpha$ (one-sided)	
Equivalence limit difference, <math>\bar{x}_0</math>	10.000
Expected difference, <math>\bar{x}_1</math>	0.000
$\bar{x}_0 - \bar{x}_1$	10.000
Common standard deviation, <math>\sigma</math>	25.000
Effect size, <math>\delta =  \bar{x}_0 - \bar{x}_1  / \sigma</math>	0.400
Power ( % )	80
n per group	100

### Secondary outcome measure:

To show superiority of TAP to No TAP a two group t-test with a 0.05 two-sided significance level will have 88% power to detect the difference between a Control Group 1 (No TAP block) mean,  $\bar{x}_1$ , of 60 mg morphine use in the first 24 hours after surgery and a Group 2 (TAP block) mean,  $\bar{x}_2$ , of 45 mg morphine, a difference in means of 15, assuming that the common standard deviation is 25 mg, when the sample sizes in the two groups are 40 and 100, respectively.

Thus total number of patients to show non-inferiority between ultrasound-guided and laparoscopic-guided TAP block, and superiority of either technique to no TAP is 240 patients. Allowing for a 5% drop out rate (n=12 patients), the total number of patients we anticipate to recruit is 252.

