### **II. In the preoperative holding area:**

- a) An anesthesia investigator assigned to the specific case will assess patients and perform a pre-operative anesthesia assessment as per standard protocol at CSMC. None of this data will be recorded until written informed consent is obtained.
- b) Patients will provide a detailed medical history including demographic information (e.g., age, weight, height, ethnic origin, smoking history, history of motion sickness, history of postoperative nausea and vomiting, as well as chronic analgesic usage). None of this data will be recorded until written informed consent is obtained.
- c) Written informed consent will be obtained by one of the investigators.
- d) Patients will be randomized in a blinded fashion by study staff to one of the groups via online randomization site, sealedenvelope.com, in a 2:2:1 fashion.

Group 1	n=100	Ultrasound guided TAP Block
Group 2	n=100	Laparoscopic guided TAP Block
Group 3	n=40	No TAP

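### The TAP versus No TAP t-test is sized on one common SD at 40 versus 100 and its variance form is not stated; naming Welch is a cheap improvement

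*Combined protocol and SAP*

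**What the plan says.** The Data Analysis section, under the secondary outcome measure, holds the only analysis text for TAP against No TAP. It states that "a two group t-test with a 0.05 two-sided significance level will have 88% power to detect the difference". The planning means are 60 mg for No TAP and 45 mg for TAP, which leaves 15 mg to be detected. The sizing is done "assuming that the common standard deviation is 25 mg, when the sample sizes in the two groups are 40 and 100". The same section takes the total needed for non-inferiority and for "superiority of either technique to no TAP is 240 patients", so each TAP arm of 100 is to be set against the 40.

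The allocation table in Study Methods, section II, agrees on the small arm ("Group 3 n=40 No TAP"), although the sentence above that table randomises "in a 2:2:1 fashion".

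Nowhere do the documents mention a separate-variance test, a transformation, a rank test or a sensitivity analysis for this comparison. Nor do they mention a confidence interval for it.

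**The concern.** The pooled t-test tolerates unequal SDs when the groups are the same size, as in the 100 versus 100 comparison of the two TAP techniques. It does not when one group is 2.5 times the other. The pooled variance is then dominated by the larger arm, while the true variance of the difference is dominated by the smaller one.

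Unequal SDs are plausible here. Opioid totals cannot be negative, so their spread often grows with the mean, and the plan expects the higher mean in the 40-patient arm. That would make a pooled interval too narrow. The opposite is also possible: a mix of working and failed blocks could make the TAP arms more variable, and a pooled interval would then be too wide and power would be lost.

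The analysis section labels this comparison secondary, but the first study objective includes the no-block arm and the stated hypothesis claims superiority of both techniques over it. The size of the benefit and its uncertainty will be a main result.

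**Working it through.** **Inputs from the plan (Data Analysis, secondary outcome measure).** n = 40 and 100; difference 60 − 45 = 15 mg; common SD 25 mg; two-sided alpha 0.05; stated power 88%.

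**Step 1: the plan's own figure.** SE = 25 × √(1/40 + 1/100) = 25 × √0.035 = 4.677 mg. Noncentrality = 15/4.677 = 3.21. The noncentral t with 138 degrees of freedom gives 89.0%; the normal approximation gives 89.4%. The stated 88% is reproduced to within about 1 point, under equal SDs.

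**Step 2: pooled against true standard error.** With SD s₁ in No TAP and s₂ in TAP:

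- True SE = √(s₁²/40 + s₂²/100)
- Pooled SE = √{[(39 s₁² + 99 s₂²)/138] × 0.035}

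The case 33.3/25 assumes the same coefficient of variation in both arms: 25 × 60/45 = 33.3. Then:

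- True SE = √(27.72 + 6.25) = 5.83 mg
- Pooled variance = (39 × 1108.9 + 99 × 625)/138 = 761.8, so pooled SE = √(761.8 × 0.035) = 5.16 mg
- Ratio 5.16/5.83 = 0.886, so the pooled SE is about 11% too small.

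**Step 3: coverage and rejection rates.** Simulation with normal data, at least 400,000 trials per case. All unequal SDs are assumptions. Rejection is at a true difference of 15 mg.

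| SD No TAP/TAP | True SE | Pooled SE | Coverage, pooled | Coverage, Welch | Rejection, pooled | Rejection, Welch |
|---|---|---|---|---|---|---|
| 25/25 | 4.68 | 4.68 | 95.0% | 95.0% | 88.9% | 88.5% |
| 30/25 | 5.36 | 4.96 | 93.0% | 95.0% | 83.2% | 78.6% |
| 33.3/25 | 5.83 | 5.16 | 91.7% | 95.0% | 79.4% | 71.6% |
| 37.5/25 | 6.44 | 5.44 | 90.3% | 95.0% | 74.4% | 62.9% |
| 25/30 | 4.96 | 5.37 | 96.5% | 95.0% | 81.0% | 84.7% |
| 25/33.3 | 5.17 | 5.84 | 97.3% | 95.0% | 74.7% | 81.8% |

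**Step 4: what this means for type I error.** With fixed SDs, type I error is 100% minus coverage: 7.0% at 30/25 and 8.3% at 33.3/25. Those rates apply only if the SDs differ while the means are equal. If the SD is proportional to the mean, equal means imply equal SDs, and the pooled test keeps its 5%. The error then appears only as interval coverage when TAP has a true effect.

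**Step 5: is it specific to the unequal comparison?** At 100 versus 100 the pooled and true SE coincide for any pair of SDs (4.16 mg for both at 33.3/25) and type I error stays at 5.0%. At 48 versus 96, which is what 2:2:1 gives for 240 patients, pooled coverage at 33.3/25 is 92.6% and at 30/25 is 93.5%. The effect is smaller but does not vanish.

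**The case against.** The strongest reply is that the plan never commits to pooling. The common SD is an input to a power statement, and a two-group t-test can be run with separate variances. This stands. A reader might infer from the sizing text that a wrong standard error is planned, but the documents show only that the variance form is left open. What remains is that the unqualified name usually means the pooled test, that the power figure is reproduced in that form, and that nothing stops the choice being made after the data are seen.

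A second reply is that no confidence interval is planned for this comparison, so none can be wrong. That is true of the text. Coverage is used here to measure whether the standard error is right, and an interval should be reported in any case.

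Third, a reader might infer a false-positive rate of 7% to 10%. The argument that spread rises with the mean does not support this, because it gives equal SDs under the null. Such rates need SDs that differ at equal means, and the documents give no evidence either way.

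Fourth, Welch is not free. If No TAP is the more variable arm it rejects less often than the pooled test: about 72% against 79% at 33.3/25. Where the SD scales with the mean, so that the pooled test keeps its 5% level, that is a real loss. It is offset by a gain in the other direction: about 82% against 75% at 25/33.3.

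**Conclusion.** This is a cheap improvement to an under-specified analysis. It does not show that the planned result would be wrong. The stated 88% power is sound for SD 25 in both arms. If the test is run pooled at 40 versus 100 and the SDs differ, nominal 95% coverage is about 93.0% at No TAP/TAP SDs of 30/25, 91.7% at 33.3/25 and 97.3% at 25/33.3. Welch stays at about 95% throughout.

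The arithmetic is firm. Its relevance rests on assumed SDs, since the documents give none by arm, and on the test being run in pooled form. The direction of any error cannot be known in advance, and for a modest SD difference (30 against 25) the shift is about 2 points of coverage. The documents do not support the stronger conclusions that pooling is prescribed, that a planned interval is invalid, or that the false-positive risk is generally raised.

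**What to change.** In Data Analysis, under the secondary outcome measure, add that every comparison involving the No TAP arm will use the Welch (unequal-variance) t-test and will report the difference in means with its Welch 95% confidence interval. Add that the 88% power holds only if the SD is 25 mg in both arms; with Welch it would be about 72% at 33.3/25.

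The cost is one or two sentences, with no extra patients or data. Power falls by about 0.4 points if the SDs are equal (88.9% to 88.5%). If they are not, the rejection rate relative to the pooled test falls when No TAP is more variable (79% to 72% at 33.3/25) and rises when TAP is more variable (75% to 82% at 25/33.3).

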## SUBJECT RECRUITMENT

1. The subjects will be approached regarding the study during their preoperative consultation visit. If patient indicates a willingness to participate and meets the inclusion criteria and does not meet any exclusion criteria, they will be handed, emailed, or mailed a copy of the consent form to read, and the study will be scheduled at least 24 hours after they have received the consent form to review. The consent form will detail the purposes,

procedures, possible risks and benefits of the study. The informed consent form will have a contact number for the investigators to allow subjects to ask questions prior to the day of surgery.

2. Subjects must give informed consent to participate in the study.
3. When the patient arrives for the surgery, a study investigator will meet with the patient and discuss the procedure in detail in the preoperative holding area, and provide another copy of the informed consent for the patient to review and sign.
4. After the patient has signed informed consent, they will be randomized to one of three study arms by the study staff.

## **INCLUSION CRITERIA**

A total of 252 patients undergoing laparoscopic colorectal procedures

Willingness and ability to sign an informed consent document

No allergies to anesthetic or analgesic medications

ASA physical status Class I – III adults of either sex

Aged 18-90 years

## **EXCLUSION CRITERIA**

Patients who demonstrate any one of the following will be excluded from the study:

1. Refusal to participate in the study
2. Age <18 or > 90 years
3. Contraindications to regional blockage including but not limited to:
  - a. Patient refusal to regional blockade
  - b. Infection at the site of needle insertion
  - c. Systemic infection
  - d. Bleeding diathesis or coagulopathy (as diagnosed by history or laboratory evaluation)

## **BENEFITS TO STUDY SUBJECTS**

TAP block techniques are well described in patients undergoing colorectal surgery procedures and with demonstrable benefit with respect to narcotic sparing pain relief. The benefit for our participants will be that these techniques will demonstrate enhanced duration of analgesia, reduction in opioid intake and a concomitant reduction in side effects. All of this should improve patient satisfaction.

**COMPENSATION:** There is no compensation for study participants.

**POTENTIAL RISKS:** There are the following risks associated with this prospective observational study.

- A. Local Anesthetics: Inadvertent intravascular injection with resultant local anesthetic toxicity could result. Direct visualization, frequent aspiration and inclusion of epinephrine as a marker; make the incidence of this very low. In the setting of an inadvertent intravascular injection, Intralipid is readily available and has been shown to be very effective in reducing morbidity and mortality from LAST (Local Anesthetic Systemic Toxicity).
- B. Transversus abdominis plane block. Inadvertent intravascular injection is a potential risk associated with any regional technique. This is seen in less than 0.01% of patients and that percentage is further mitigated with direct visualization under ultrasound guidance.
- C. Epinephrine 1:200,000 produce a minimal risk of vasoconstriction (it is used as a marker to reduce the incidence of inadvertent intravascular injection).
- D. Injection site hematoma, ecchymosis, bleeding. Ultrasound guidance and laparoscopic guidance will allow investigators visualization to avoid puncture of blood vessels and subsequent hematoma. Patients with known bleeding diathesis or those on therapeutic anticoagulation will be excluded from the study.
- E. Injection site infection. Sterile technique will minimize this complication. Investigators will monitor the injection site for signs of infection including erythema, drainage, pain, tenderness or fluctuance.
- F. Pain at the injection site. Small needles are used to perform the injection and therefore minimizing associated pain at the injection site.

**MAINTAINANCE OF CONFIDENTIALITY:** Patients' names will not be divulged and all data will be coded in the study records. Information gained during the course of the study will only be used by the investigators for the purpose of this study and no patient names or other identifying data will be used in any future publications.

#### **PROCEDURES TO MAINTAIN CONFIDENTIALITY**

All data will be coded and patient's name will not be disclosed in any of the study records according to standard HIPAA policy. All the information gained during the course of the study will be used by the investigator for the evaluation of the purpose of this study in patients

undergoing outpatient surgery. No patient names (or other identifying data) will be used in any further publication.

## **DATA ACCURACY AND PROTOCOL COMPLIANCE**

1. Obtaining Informed Consent: A study investigator will first insure subject eligibility, and upon confirmation of this, obtain informed consent from the subject in an interview. Assurance of “informed” consent will be performed by discussing the study with the subject, and providing the patient a copy of the consent form.
2. Maintaining Confidentiality: Once enrolled in this study, each participating subject will be assigned a unique numerical identifier, with all other identifying information removed. Subjects’ names will not be divulged and all data will be coded in the study records. A master list of enrolled subjects will be kept in a locked and secure room, in a locked and secure building, directly accessible only by the study investigators. Authorized research personnel access to any identifying information will be restricted to the minimal level needed for performance of the study. No patient names (or other identifying data) will be used in any future publication(s).
3. Quality Control for Data Accuracy:
  - a. Subject eligibility: Each potentially eligible subject referred to the study will first undergo evaluation by a study investigator regarding whether patient meets inclusion criteria and any exclusion criteria. This will be done with direct referring physician interview, direct subject interview, and focused medical record review.
  - b. Subject demographic data and questionnaire: Collected by study investigator through direct subject interview and focused medical record review.
  - c. Laboratory samples: None will be collected

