## **STUDY OBJECTIVES**

1. The primary objective of this study is to compare ultrasound-guided block of the transversus abdominis plane (TAP) vs. laparoscopic-guided TAP block, versus no TAP block on opioid consumption in the first 24 hours following colorectal surgery.
2. The secondary objective of this study is to assess the impact of these adjunctive regional techniques on overall patient satisfaction, postoperative pain scores, length of postoperative hospital stay, postoperative ileus, and adverse events directly related or unrelated to TAP block in the 30-day postoperative period.

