## **STUDY METHODS**

### **I. Recruitment**

- a) Patients of the investigators will be recruited for this study during their preoperative outpatient appointments approximately one week before surgery. The study material packet containing the HIPAA and the informed consent form will be emailed to the patient for review. Thus the patient will have adequate time to ask questions and consider the study prior to scheduled surgery.
- b) The patients will be contacted by one of the study investigators the morning of surgery at which time a signed consent will be obtained.
- c) Only patients who have provided their written consent and indicated that they have been introduced to the study prior to meeting with the anesthesiologists on the day of surgery will be able to participate.
- d) Screening procedures will make sure patients meet all inclusion criteria.

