### III. During the intraoperative period

- a) Standard anesthesia monitors will be applied: automatic blood pressure cuff, three-lead electrocardiography, capnography, and pulse oximetry will be used continuously.
- b) Induction of general anesthesia will be with propofol 2-3 mg/kg & a non-depolarizing muscle relaxant (choice will be operator dependent). Maintenance of anesthesia will be with an inhalational anesthetic.
- c) The study staff performing randomization will instruct the anesthesiologist or surgeon to either block the transversus abdominis plane with ultrasound, laparoscopy, or no block.
- d) For the block, a standard weight based dose (bupivacaine 0.25% with epinephrine 1:200,000, at a 1ml/kg dose) will be used for both ultrasound-guided or laparoscopic-guided block.
- e) The block is administered between the costal margin and iliac crest in the anterior axillary line at 2 different sites on each side (4 injections total).
- f) For ultrasound-guided TAP block, after the surgeons have completed their portion of the procedure, a member of the anesthesia research team will use sterile technique to prep the abdomen. The block is then placed bilaterally (at 2 different sites on each side of the abdomen) in the anterior axillary line, between the costal margin and iliac crest in the intermuscular plane between the internal oblique and transversus abdominis muscles using ultrasound guidance.
- g) For laparoscopic-guided TAP block, the attending surgeon will perform the block at the conclusion of the procedure under laparoscopic guidance. Bilateral TAP block will be performed in the anterior axillary line between the costal margin and iliac crest. After the needle is passed through the skin, it is continued until 2 distinct “pops” are felt, indicating the needle pierced each of the 2 fascia layers (external oblique and internal oblique fascia).

After injection of the correct plane, a smooth raised area of fluid covered by transversus abdominis muscle is seen with the laparoscope. The laparoscopic vision also assures that the preperitoneal plane is not injected and that the injection does not go intraperitoneal.

- h) Dose of anesthetics, analgesics, local anesthetics, and IV fluid therapy during the operation will be recorded in the anesthesia record as per standard procedure. A copy of the sonographic image will be collected for each patient at the conclusion of the block.

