#### VI. Patient evaluation during hospital admission:

- VRS for pain assessment will be utilized to assess pain within the first 72 hours postoperatively and pain scores will be recorded in the patient chart by the nursing staff as per routine CSMC protocol. The average pain scores will be calculated for study analysis.
- VRS scores along with dose for all opioids will be recorded.
- Physical signs and symptoms related to the peripheral nerve block (residual sensory blockade) will be noted.

- Patient satisfaction with the overall technique will also be queried.

Pain evaluation recorded by nursing staff as per standard CSMC guidelines:

- At PACU every 30 minutes
- During admission: 12, 24, 48, and 72 hours postoperatively

Patient satisfaction with analgesia will be assessed at the time of hospital discharge or within 30 days postoperatively by telephone using a patient satisfaction survey:

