### **Pain Management Satisfaction Survey**

On a scale of 1-5, how satisfied were you with your postoperative pain management?

Very Unsatisfied	Somewhat Dissatisfied	Neutral	Somewhat Satisfied	Extremely Satisfied
1	2	3	4	5

1 = very unsatisfied.

5 = extremely satisfied.

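### The satisfaction rating appears to be collected by a study investigator in interview, and nothing requires that interviewer to be unaware of the arm

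*Combined protocol and SAP*

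**What the plan says.** **Who collects it.** DATA ACCURACY AND PROTOCOL COMPLIANCE, item 3b: "Subject demographic data and questionnaire: Collected by study investigator through direct subject interview and focused medical record review".

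**When and how.** Section VI (Patient evaluation during hospital admission) has satisfaction assessed "at the time of hospital discharge or within 30 days postoperatively by telephone using a patient satisfaction survey". It does not say who asks.

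**The instrument.** The Pain Management Satisfaction Survey is one item: "On a scale of 1-5, how satisfied were you with your postoperative pain management". Its five response levels are labelled from very unsatisfied to extremely satisfied.

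**Its standing.** The secondary objective under STUDY OBJECTIVES is to "assess the impact of these adjunctive regional techniques on overall patient satisfaction, postoperative pain scores", among other outcomes. STUDY DESIGN also lists satisfaction as a secondary outcome.

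**Who the investigators are.** Section I (Recruitment): "Patients of the investigators will be recruited for this study". Section II has an anesthesia investigator allotted to each case for the preoperative assessment.

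**Who knows the arm.** Under section III, study staff tell the anesthesiologist or surgeon which technique to use, if any. In the laparoscopic arm "the attending surgeon will perform the block at the conclusion of the procedure under laparoscopic guidance". In the ultrasound arm the operator comes from the anesthesia research team.

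**Blinding.** STUDY DESIGN describes the patient as blinded and mentions no one else. Section II uses the word blinded for the act of randomizing, not for outcome collection.

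**The concern.** A satisfaction rating is subjective, and the answer can depend on who asks. A patient asked by someone involved in their care may give a more courteous answer. An interviewer who knows the arm may also prompt or record differently according to arm, without intending to. Blinding the patient removes the patient's own expectation about the technique, but not the interviewer's influence.

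The plan also states the direction it expects. BACKGROUND AND SIGNIFICANCE hypothesizes that either block beats no block, and BENEFITS TO STUDY SUBJECTS anticipates better satisfaction. The operator's specialty differs between the two block arms, so an interviewer from either specialty could be associated with one technique. If the influence differed by arm, a difference in satisfaction could appear, or be hidden, for reasons unrelated to the blocks. The ratings could not be collected again without it.

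**Working it through.** The documents give no figure on this point, so there is none to reproduce. The sample-size calculations under Data Analysis concern morphine use and do not depend on it. The check is mainly a reading of the sections together.

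**Step 1. Does item 3b cover the satisfaction item?** It speaks only of a questionnaire and pairs it with demographic data. The satisfaction survey is the only questionnaire defined in the documents. That it is the one meant is a strong inference, not an explicit statement.

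**Step 2. Might the interviewer know the arm?** Item 3b names a study investigator. Sections I to III show that investigators include clinicians caring for these patients and that the case anesthesiologist or surgeon is told the allocation. An investigator told the arm is therefore eligible to interview. No section says that the interviewer must be such a person, or must not be.

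**Step 3. Is there a safeguard elsewhere?** None was found: no interviewer blinding, no separation from the treating team, no script and no self-completion.

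**Step 4. When would this distort a comparison?** Let the interviewer effect be b1 in one arm and b2 in another. The observed difference is the true difference plus (b1 − b2). If b1 = b2, the effect cancels. Only the differential part, b = b1 − b2, matters.

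**Step 5. Illustration on assumed values.** Neither the SD of the rating nor b is in the documents, and Data Analysis names no test for satisfaction. Assume a two-sided 5% comparison of means by normal approximation, no true difference, an SD of 0.8 to 1.2 points and b of 0.1 to 0.3 points. Group sizes (100, 100, 40) are from section II.

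- SE = SD × √(1/n₁ + 1/n₂)
- False-positive rate = 1 − Φ(1.96 − b/SE) + Φ(−1.96 − b/SE)

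Example: SD 1.0, 100 vs 100, b = 0.2. SE = √(2/100) = 0.141 and b/SE = 1.414. The rate is 1 − Φ(0.546) + Φ(−3.374) = 0.293.

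| SD | b | 100 vs 100 | 40 vs 100 |
|---|---|---|---|
| 0.8 | 0.1 | 14.3% | 10.3% |
| 0.8 | 0.2 | 42.4% | 26.7% |
| 0.8 | 0.3 | 75.5% | 51.8% |
| 1.0 | 0.1 | 10.9% | 8.3% |
| 1.0 | 0.2 | 29.3% | 18.8% |
| 1.0 | 0.3 | 56.4% | 36.1% |
| 1.2 | 0.1 | 9.1% | 7.3% |
| 1.2 | 0.2 | 21.8% | 14.5% |
| 1.2 | 0.3 | 42.4% | 26.7% |

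The table shows that a small differential effect would matter if there were one. It is not evidence that there is one.

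**The case against.** The strongest reply is that item 3b may not concern the satisfaction survey. It follows the eligibility item, pairs the questionnaire with demographics and allows record review, which cannot supply a satisfaction rating. It could describe the preoperative history in section II, item b. This stands as a reason to write that the plan appears to use an investigator interview. It does not dispose of the point: on that reading, nothing says who collects the survey, and a blinded collector is still not required.

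Second, a reader might infer that the plan has an unblinded treating clinician interview each patient. The documents do not support that. Study investigators are a wider group than the clinicians told the arm for a given case, and an investigator unaware of it could do the interview. What stands is that this is left to chance.

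Third, a reader might infer that the ratings will favor one technique. General courtesy inflation is common to all arms and cancels. Every patient has both a surgeon and an anesthesiologist, and nothing links the interviewer's identity to the arm. The patient is blinded, and one fixed question about pain management overall leaves limited room for influence. All of this stands; it lowers the risk without removing it.

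Fourth, the percentages rest on an assumed SD, assumed shifts and a test that the plan does not specify. That is correct, and they should not be read as error rates of this trial.

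**Conclusion.** The concern holds as a risk, not as a demonstrated bias. On the most natural reading of item 3b, a study investigator collects the satisfaction item in direct interview. Investigators include clinicians who may know the arm, and no section requires the interviewer not to know it. The outcome is open to interviewer bias, which would distort an arm comparison only if it differed by arm.

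Its size cannot be derived from the documents. Under the assumptions above, a differential shift of 0.2 points would turn a 5% error rate into about 22-42% between the block arms and 15-27% for a block arm against no block.

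The reach is narrow: one single-item secondary outcome. A reader might extend the point to the trial's main result, but the primary outcome is opioid use over 24 hours, and nursing staff record the pain scores (sections IV and VI), so neither is touched by this route. Severity is minor; this is a cheap improvement.

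**What to change.** Amend section VI and DATA ACCURACY AND PROTOCOL COMPLIANCE, item 3b, together:

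- State that item 3b's interview rule does not apply to the satisfaction survey.
- Have the patient complete the single item alone, on paper or electronically, by default at discharge, with no investigator administering it.
- Keep the telephone for patients missed at discharge. Read the item verbatim from a fixed script, where feasible by existing personnel who did not treat the patient and were not told the allocation.
- Record for each patient which mode was used.

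**Cost.** Self-completion needs one form and a wording change, and is nearly free. The telephone part is less simple: the study staff who randomize and pass on the allocation know the arm, so a caller unaware of it may not always be available without extra staff. That is why it is asked for only where feasible.

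**Downside.** A few forms may not be returned, and some calls may still be made by someone who knows the arm. The recorded mode lets those ratings be identified.
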